- 14. Blood sampling for B-cell assessment at the first infusion date of the third course will be performed at predose (before administration [within 15 minutes prior to the beginning of the study drug infusion]), end of infusion (within 15 minutes after the end of the study drug infusion), and at 1 hour [±15 minutes] after the end of the study drug infusion. If Extension Week 0 is conducted on the same day with Week 48, the predose result from the B-cell samples obtained according to the scheduled schemes for Extension Week 0 (Table 9) will be the result of B-cell kinetics at Week 48.
Protocol Number CT-P10 3.2

- 15. Throughout the study, patients will be monitored for the clinical signs and symptoms of TB, and interferon-γ release assay can be performed at the investigator's discretion based on the judgment on the signs and symptoms of TB monitoring.
- 16. Adverse events will be assessed from the date the ICF is signed until the last assessment date or End of Study Visit.

Study Period					PD			Safety		
Week	Day	PK for Part 1	PK for Part 2	B-Cell Kinetics	CRP, ESR	RF, anti-CCP	Immuno- globulin	Immuno- genicity	Hematology, Clinical Chemistry, Urinalysis	
	0	Predose ¹ ; end of infusion ² ; 1 hour after end of infusion ³	Predose ¹ ; end of infusion ² ; 1 hour after end of infusion ³	Predose ¹ ; end of infusion ² ; 1 hour after end of infusion ³	Pretreatment ⁴	NA	Pretreatment ⁴	Pretreatment ⁴	Pretreatment ⁴	
0	1	24 hours after start of infusion ⁵	NA	24 hours after start of infusion ⁵ (only for patients from Part 1)	NA	NA	NA	NA	NA	
1	7	Time not specified ⁶	NA	Time not specified ⁶	NA	NA	NA	NA	NA	
2	14	Predose ¹ ; end of infusion ² ; 1 hour after end of infusion ³	Predose ¹ ; end of infusion ² ; 1 hour after end of infusion ³	Time not specified ⁶	NA	NA	NA	NA	Pretreatment ⁴	
	15	24 hours after start of infusion ⁵	NA	NA	NA	NA	NA	NA	NA	
3	21	Time not specified ⁶	NA	Time not specified ⁶	NA	NA	NA	NA	NA	
4	28	Time not specified ⁶	NA	Time not specified ⁶	Time not specified ⁶	NA	NA	NA	NA	

Table 7	Sampling Times for Pharmacokinetic, Pharmacodynamic, and Safety Assessments for the Main Study Period
	(for patients who receive both first and second courses of treatment)

Protocol Version 5.1, including Country-Specific Protocol Amendment 1 (US) – 01 April 2016

Protocol Number CT-P10 3.2

Study Period				PD			Safety		
Week	Day	PK for Part 1	PK for Part 2	B-Cell Kinetics	CRP, ESR	RF, anti-CCP	Immuno- globulin	Immuno- genicity	Hematology, Clinical Chemistry, Urinalysis
8	56	Time not specified ⁶	NA	Time not specified ⁶	Time not specified ⁶	NA	Time not specified ⁶	NA	Time not specified ⁶
12	84	Time not specified ⁶	NA	Time not specified ⁶	Time not specified ⁶	NA	NA	NA	NA
16	112	Time not specified ⁶	NA	Time not specified ⁶	Time not specified ⁶	NA	Time not specified ⁶	NA	Time not specified ⁶
20	140	NA	NA	NA	Time not specified ⁶	NA	NA	NA	NA
24	168	Predose ¹ ; end of infusion ² ; 1 hour after end of infusion ³	Predose ¹ ; end of infusion ² ; 1 hour after end of infusion ³	Predose ¹ ; end of infusion ² ; 1 hour after end of infusion ³	Pretreatment ⁴				
26	182	Predose ¹ ; end of infusion ² ; 1 hour after end of infusion ³	Predose ¹ ; end of infusion ² ; 1 hour after end of infusion ³	Time not specified ⁶	NA	NA	NA	NA	Pretreatment ⁴
32	224	NA	NA	Time not specified ⁶	Time not specified ⁶	NA	Time not specified ⁶	NA	Time not specified ⁶
40	280	NA	NA	Time not specified ⁶	Time not specified ⁶	NA	Time not specified ⁶	NA	Time not specified ⁶
48	336	Time not specified ⁶	Time not specified ⁶	Time not specified ⁶	Time not specified ⁶	Time not specified ⁶	Time not specified ⁶	Time not specified ⁶	Time not specified ⁶
EOS ⁷		Time not specified ⁶	Time not specified ⁶	Time not specified ⁶	Time not specified ⁶	Time not specified ⁶	Time not specified ⁶	Time not specified ⁶	Time not specified ⁶

Abbreviations: anti-CCP, anti-cyclic citrullinated peptide; CRP, C-reactive protein; EOS, end of study; ESR, erythrocyte sedimentation rate; NA, not applicable; PD, pharmacodynamic; PK, pharmacokinetic; RF, rheumatoid factor.

Protocol Version 5.1, including Country-Specific Protocol Amendment 1 (US) - 01 April 2016

Protocol Version 5.1

Protocol Number CT-P10 3.2

Protocol Version 5.1

- * IMPORTANT! For patients who receive the third course of treatment at Week 48, the samples should be obtained according to the sampling schemes for the Extension Week 0 provided in the Table 9. Otherwise, all scheduled samplings for Week 48 should be performed separately from the Extension Week 0 according to this sampling scheme.
- 1. Predose: Blood samples will be obtained within 15 minutes prior to the beginning of the study drug infusion.
- 2. End of infusion: Blood samples will be obtained within 15 minutes after the end of study drug infusion.
- 3. 1 hour after end of infusion: Blood samples will be obtained 1 hour (±15 minutes) after the end of study drug infusion on dosing days.
- 4. Pretreatment: Blood samples will be obtained prior to the study drug infusion.
- 5. 24 hours after start of infusion: Blood samples will be obtained 24 hours (±2 hours) after the start of study drug infusion.
- 6. Time not specified: Blood samples will be obtained any time during the day.
- 7. The EOS Visit only needs to be completed if the patient withdraws prior to study completion. End-of-study assessments should be completed at least 8 weeks after the last study drug infusion and before Week 48 of Study Period if a patient withdraws prior to the completion of Week 48 visit. If the patient has completed by Week 48 of Study Period, an EOS Visit is not required.

Table 8Sampling Times for Pharmacokinetic, Pharmacodynamic, and Safety
Assessment for the Main Study Period between Weeks 24 and 48 (for
patients who receive only first course of treatment)

Study Period				PD		Safety			
Week	Day	РК	B-Cell Kinetics	CRP, ESR	RF, anti-CCP	Immuno- globulin	Immuno- genicity	Hematology , Clinical Chemistry, Urine	
24	168	Time not specified ¹							
32	224	NA	Time not specified ¹	Time not specified ¹	NA	Time not specified ¹	NA	Time not specified ¹	
40	280	NA	Time not specified ¹	Time not specified ¹	NA	Time not specified ¹	NA	Time not specified ¹	
48	336	NA	Time not specified ¹						
EOS ²		NA	Time not specified ¹						

Abbreviations: anti-CCP, anti-cyclic citrullinated peptide; CRP, C-reactive protein; EOS, end of study; ESR, erythrocyte sedimentation rate; NA, not applicable; PD, pharmacodynamic; PK, pharmacokinetic; RF, rheumatoid factor.

* IMPORTANT! For patients who receive the third course of treatment at Week 48, the samples should be obtained according to the sampling schemes for the Extension Week 0 provided in the Table 9. Otherwise, all scheduled samplings for Week 48 should be performed separately from the Extension Week 0 according to this sampling scheme.

1. Time not specified: Blood samples will be obtained any time during the day.

2. The EOS Visit only needs to be completed if the patient withdraws prior to study completion. End-of-study assessments should be completed at least 8 weeks after the last study drug infusion and before Week 48 of study period if a patient withdraws prior to the completion of Week 48 visit. If the patient has completed by Week 48 of the Study Period, an EOS Visit is not required.

Study Period			PD		Safety			
Ext Week	Ext Day	B-Cell Kinetics	CRP, ESR	RF, anti-CCP	Immuno- globulin	Immuno- genicity	Hematology, Clinical Chemistry, Urinalysis	
0	0	Predose ¹ ; end of infusion ² ; 1 hour after end of infusion ³	Pretreatment ⁴					
2	14	Pretreatment ⁴	NA	NA	NA	NA	Pretreatment ⁴	
8	56	Time not specified ⁵	Time not specified ⁵	NA	Time not specified ⁵	Time not specified ⁵	Time not specified ⁵	
16	112	Time not specified ⁵	Time not specified ⁵	NA	Time not specified ⁵	Time not specified ⁵	Time not specified ⁵	
24	168	Time not specified ⁵	Time not specified ⁵	Time not specified ⁵	Time not specified ⁵	Time not specified ⁵	Time not specified ⁵	
EOS ⁶		Time not specified ⁵	Time not specified ⁵	Time not specified ⁵	Time not specified ⁵	Time not specified ⁵	Time not specified ⁵	

Table 9Sampling Times for Pharmacodynamic, and Safety Assessments for the
Extension Study Period

Abbreviations: anti-CCP, anti-cyclic citrullinated peptide; CRP, C-reactive protein; EOS, end of study; ESR, erythrocyte sedimentation rate; NA, not applicable; PD, pharmacodynamic; RF, rheumatoid factor.

1. Predose: Blood samples will be obtained within 15 minutes prior to the beginning of the study drug infusion.

2. End of infusion: Blood samples will be obtained within 15 minutes after the end of study drug infusion.

3. 1 hour after end of infusion: Blood samples will be obtained 1 hour (±15 minutes) after the end of study drug infusion on dosing days.

- 4. Pretreatment: Blood samples will be obtained prior to the study drug infusion.
- 5. Time not specified: Blood samples will be obtained any time during the day.

6. The EOS Visit only needs to be completed if the patient withdraws prior to study completion. End-of-study assessments should be completed at least 8 weeks after the last study drug infusion and before Extension Week 24 if a patient withdraws prior to the completion of Extension Week 24 visit. If the patient has completed the Study Period, a separate EOS Visit is not required. In this case, the last visit will be considered the EOS Visit.

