In Part 2, approximately 172 subsequent patients with RA will be randomly assigned in a 1:1 ratio to 1 of 2 treatment groups, CT-P10 or Rituxan. In total, approximately 361 patients will be available for analysis.

The first approximately 189 patients to be enrolled in the study will be assigned to Part 1 and all subsequent patients enrolled in the study will be assigned to Part 2. All patients from Part 1 of the study will be included in Part 2 of the study and undergo all assessments performed in Part 2. A schematic of study patient assignment for Part 1 and Part 2 is presented in Figure 2. Part 2 will run independently and in parallel with Part 1.

Figure 2 Schematic Diagram of Study Patients for the Main Study Period (up to Week 48)

The Extension Study Period is designed to evaluate additional safety and immunogenicity.

Patients can continue on the Extension Study Period with an additional course of treatment regardless of the number of treatment courses they are treated during the Main Study Period if the following conditions are met;

- Complete all of the scheduled visits up to Week 48 and
- Meet the predefined safety criteria.

The third course of treatment should be initiated between Week 48 and Week 52. If administration of the third course of treatment is deemed necessary to be initiated after Week 52 at the discretion of the investigator, the study infusion can be administered within 72 weeks from the first infusion of the first course of treatment after discussion with the Sponsor. In this case, the study infusion must be initiated **NO LATER** than 52 weeks from the Day 0 for the last enrolled patient.

Note that patients, who have the End-of-Study (EOS) visit at Week 48, can participate in the Extension Study Period if the patients sign an informed consent form within 24 weeks from the EOS visit and do not have prohibited medications prior to entering the Extension Study Period.

All patients eligible for Extension Phase from Rituxan group will be randomized again at Extension Week 0. The randomization will be conducted and stratified by:

- The number of courses they are treated during the Main Study Period and
- The EULAR-CRP response status (responder vs non-responder) assessed at Week 40.

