All patients will receive MTX and folic acid concomitantly. Each patient may receive 3 courses of treatment; the first course will be an infusion of study drug (CT-P10, Rituxan or MabThera) at Week 0 and Week 2. If patients meet the predefined safety criteria, patients are eligible to receive the additional course(s) of study drug (2 infusions in each course of 2-week interval) at the discretion of the investigator. For the second course of treatment in the Main Study Period, patients, who do not meet the predefined safety criteria, will not receive an additional course of treatment, but they will be followed according to the schedule of events (Table 5) for the Main Study Period.

For the third course of treatment in the Extension Study Period, patients, who do not meet the predefined safety criteria within the time frame for the study drug infusion, will not receive an additional course of treatment and will be terminated from the study.

Safety criteria for the any courses of treatment after the first course are predefined as:

- Absolute neutrophil count should be $\geq 1.5 \times 10^3$ cells/µL (SI units: $\geq 1.5 \times 10^9$ cells/L), platelet count should be $\geq 75 \times 10^3$ cells/µL (SI units: $\geq 75 \times 10^9$ cells/L), asparatate aminotransferase or alanine aminotransferase should be ≤ 2.5 times upper limit of normal and levels of IgG should be ≥ 500 mg/dL (5.0g/L), at the last blood sample analysis (i.e, Week 16 for second course of treatment and within 8 weeks from the Extension Week 0 for third course of treatment).
- The patient has not developed any conditions which, in the investigators opinion, would preclude the patient receiving further courses of treatment (e.g., any new or uncontrolled disease such as, but not limited to, cardiovascular disease, or nervous system, pulmonary, renal, hepatic, endocrine or gastrointestinal disorder).

For the Main Study Period, a schedule of events for patients who receive both first and second courses of treatment (from Screening to Week 48 or End-of-Study Visit) is provided in Table 4 and a schedule of events for the patients who do not receive the second course of treatment (from Week 24 to Week 48 or End-of-Study Visit) is provided in Table 5. For the Extension Study Period, a schedule of events for patients is provided in Table 6.

A patient will be considered as having completed the study if:

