QOL (SF-36) assessment	Х	X ⁵											X ⁵				Х	Х
Rheumatoid factor	Х												X ⁵				Х	Х
Anticyclic citrullinated peptide	Х												X ⁵				Х	Х
Immunoglobulin testing ^{15,16}		X ⁵							Х		Х		X ⁵		Х	Х	Х	Х
Immunogenicity		X^5											X ⁵				Х	Х
Study drug infusion		Х			Х								Х	Х				
Hypersensitivity monitoring ¹⁷		Х			Х								Х	Х				
PK blood sampling for Part 1		X ¹⁸	X ¹⁸	Х	X ¹⁸	X ¹⁸	Х	Х	Х	Х	Х		X ¹⁸	X ¹⁸			Х	X ¹⁹
PK blood sampling for Part 2		X ¹⁸			X ¹⁸								X ¹⁸	X ¹⁸			Х	X ¹⁹
B-cell kinetics blood sampling for both Part 1 and Part 2^{16}		X ²⁰	X ²⁰	Х	Х		Х	Х	Х	Х	Х		X ²⁰	Х	Х	Х	Х	х
Biomarker $(Fc\gamma R)$ genotypes) ²¹		Х																
Previous and concomitant medications monitoring ²²	Х		X															
Adverse event monitoring ²³	X		X															

Abbreviations: ACR, American College of Rheumatology; CRP, C-reactive protein; DAS28, Disease Activity Score using 28 joint counts; ECG, electrocardiogram; eCRF, electronic case report form; EOS, end of study; ESR, erythrocyte sedimentation rate; HBcIg, hepatitis B core (total) Ig; HBsAb, hepatitis B surface antibody; HBsAg, hepatitis B surface antigen; HIV, human immunodeficiency virus; ICF, informed consent form; Ig, immunoglobulin; QOL, quality of life; SF-36, Medical Outcomes Study Short-Form Health Survey; TB, tuberculosis; Wk, Week; VAS, visual analogue scale.

CT-P10

Protocol Number CT-P10 3.2

* IMPORTANT! For patients who receive the third course of treatment at Week 48, the scheduled assessments and samplings should be performed according to the schedule of events and sampling schemes for the Extension Week 0 provided in the Table 6 and Table 9, respectively. Otherwise, all scheduled assessments for Week 48 should be performed separately from the Extension Week 0 according to this schedule of events.

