- 1. If the assessments or tests are done within 14 days from the randomization date, the omitting of that assessment or tests will be allowed. A visit window is not permitted from Day 0 to Day 21 (study drug may continue after discussion with the sponsor if a deviation occurs). A visit window of ±3 days is allowed from Week 4 to Week 24, a visit window of ±5 days is allowed thereafter, including the EOS Visit. If patients receive the second course of infusion, the first infusion will be administered at Week 24 with a visit window of ±3 days, and the second infusion should be administered after 2 weeks (14 days) from the first infusion. A visit window is not permitted on the day of second infusion in the second course of treatment (study drug may continue after discussion with the sponsor if a deviation occurs). Visit days during the second course of treatment will be calculated based on the date of the first infusion in the second course of treatment (Week 24 visit).
- 2. The EOS Visit only needs to be completed if the patient withdraws prior to study completion. End-of-study assessments should be completed at least 8 weeks after the last study drug infusion and before Week 48 of study period if a patient withdraws prior to the completion of Week 48 visit. If the patient has completed the Study Period, a separate EOS Visit is not required. In this case, the last visit will be considered the EOS Visit.
- 3. Hepatitis B surface antigen, HBsAb, and HBcIg should be assessed at Screening in all patients (mandatory). If the result is HBsAg (positive), the patient should be excluded from the study. For patients whose HBsAg is negative, HBsAb is negative or positive, and HBcIg is positive, a DNA test should be performed at Screening. If the DNA test result is positive, the patient should be excluded from the study and if the DNA test result is negative, the patient can be included. For those patients who have enrolled based on the DNA test, the DNA test will be done every 24 weeks for monitoring purposes. During the study, if hepatic symptoms are suspected, HBsAg, HBsAb, HBcIg, and DNA tests should be performed. Hepatitis C antibody and HIV-1 and -2 should be assessed at Screening in all patients (mandatory). Hepatitis and HIV testing will be performed at the central laboratory.

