Abbreviations: ACR, American College of Rheumatology; DAS28, Disease Activity Score using 28 joint counts; ECG, electrocardiogram; EOS, end of study; ESR, erythrocyte sedimentation rate; HBcIg, hepatitis B core (total) Ig; HBsAb, hepatitis B surface antibody; HBsAg, hepatitis B surface antigen; Ig, immunoglobulin; QOL, quality of life; SF-36, Medical Outcomes Study Short-Form Health Survey; TB, tuberculosis; Wk, Week; VAS, visual analogue scale.

* IMPORTANT! Assessments for hepatitis B, serum pregnancy test, hand and foot x-ray, PK blood sampling will be performed at Extension Week 0 according to this schedule of events ONLY IF patients receive the third course of treatment on the same day with Week 48.

Samples for PK at Week 48 should be obtained ONLY for patients who receive the second course of treatment during the Main Study Period and who receive the third course of treatment on the same day with Week 48. The sampling scheme for the PK is provided in the Table 7.

 The third course of treatment will be initiated between Week 48 and Week 52 of the Entire Study Period if patients become eligible according to the predefined safety criteria for the course based on the results assessed within 8 weeks from the Extension Week 0. A visit window of ±5 days is allowed throughout the study period except the day of second infusion of each course (study drug may continue after discussion with the sponsor if a deviation occurs). Visit

Protocol Version 5.1, including Country-Specific Protocol Amendment 1 (US) - 01 April 2016

Page 107

Protocol Number CT-P10 3.2

days during the treatment course will be calculated based on the date of the first infusion in the Extension Study Period. Unscheduled visit(s) can be conducted for assessment of safety criteria until the initiation of the third course of treatment.

- 2. The EOS Visit only needs to be completed if the patient withdraws prior to study completion. End-of-study assessments should be completed at least 8 weeks after the last study drug infusion and before Extension Week 24 if a patient withdraws prior to the completion of Extension Week 24. If the patient has completed the Study Period, a separate EOS Visit is not required. In this case, the last visit will be considered the EOS Visit.

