- 3. To keep the blind during the study, stratification factors, the number of courses they are treated during the Main Study Period and the EULAR-CRP response status (responder vs non-responder) assessed at Week 40, will be entered for all patients at Extension Week 0. In the case there were no EULAR-CRP response status available at week 40, the last EULAR-CRP response status assessment done between Weeks 40 and 48 will be used. Baseline values for assessment of EULAR-CRP will be the last value from screening to Day 0 (Week 0) of the study.
- 4. If hepatic symptoms are suspected during the study, HBsAg, HBsAb, HBcIg, and DNA tests should be performed. For those patients who have been enrolled based on the DNA test in the main study, the DNA test will be done at Extension Week 24 for monitoring purposes. Hepatitis testing will be performed at the central laboratory.
- 5. Assessed prior to study drug infusion
- 6. Vital signs (including blood pressure, heart and respiratory rates, and body temperature) will be measured after 5 minutes of rest (sitting).
- 7. Hematology (hematocrit, hemoglobin, red blood cell count, white blood cell count with differential, absolute neutrophil count, platelets), clinical chemistry (albumin, alkaline phosphatase, alanine aminotransferase, aspartate aminotransferase, blood urea nitrogen, calcium, chloride, cholesterol, triglycerides, creatine phosphokinase, creatinine, creatinine clearance [estimated by weight and by Cockcroft-Gault formula], gamma-glutamyl transferase, glucose, high-density lipoprotein cholesterol, lactate dehydrogenase, low-density lipoprotein cholesterol, phosphorous, potassium, sodium, total bilirubin, total protein). Testing will be performed at the central laboratory.
- 8. Urinalysis (color, pH, specific gravity, ketones, protein, glucose, bilirubin, nitrite, urobilinogen, occult blood, and microscopic examination of sediment, only if urinalysis dipstick results are abnormal). Testing will be performed at the central laboratory.

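### For patients enrolled on a negative HBV DNA test, a late third course has no scheduled DNA sample at or near dosing, and the interval between scheduled tests can reach 48 weeks against a stated 24

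*Protocol*

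**What the plan says.** Protocol Section 6.5.8 admits patients who are HBsAg negative and HBcIg positive if their screening DNA test is negative; a positive DNA test excludes them. For those admitted this way, Table 4 footnote 3 (Section 12.1) says that "the DNA test will be done every 24 weeks for monitoring purposes". Tables 4 and 5 place the test at Weeks 24 and 48.

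The Extension schedule is Table 6. Its starred note lists hepatitis B among the assessments done at Extension Week 0 "ONLY IF patients receive the third course of treatment on the same day with Week 48". When the third course is given on another day, the Table 4 note says that "all scheduled assessments for Week 48 should be performed separately from the Extension Week 0", so the DNA sample stays at Week 48. Table 6 footnote 4 then says that "the DNA test will be done at Extension Week 24 for monitoring purposes". It also calls for hepatitis B serology and DNA if hepatic symptoms are suspected. SAP Appendix 1 repeats the starred note and footnote 4.

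Section 3.1 plans the third course for Weeks 48 to 52 but allows a later start: after discussion with the sponsor, "the study infusion can be administered within 72 weeks from the first infusion of the first course of treatment". Patients whose end-of-study visit was at Week 48 may join if they "sign an informed consent form within 24 weeks from the EOS visit". A late infusion must begin no later than 52 weeks from Day 0 of the last enrolled patient.

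The passage in Section 3.1 that begins "Safety criteria for the any courses of treatment after the first course are predefined as" lists neutrophils, platelets, AST or ALT up to 2.5 times ULN, and IgG. For the third course these come from a sample within 8 weeks of Extension Week 0. It adds the investigator's opinion that no precluding condition, hepatic disorder included, has developed. HBV DNA is not in the list.

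**The concern.** The third course is a further round of B-cell depletion in patients whom the protocol itself singles out for DNA monitoring. It names new or reactivated hepatitis B among its infections of special interest (Section 6.5.10.1) and schedules DNA tests alongside liver chemistry and symptom checks. The starred note is written for the planned start at Weeks 48 to 52, where the Week 48 sample is at most 4 weeks old. It does not adapt to the later starts that Section 3.1 permits.

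For a late starter, Tables 4 to 6 schedule no visit between Week 48 and Extension Week 0. Without suspected hepatic symptoms, virus that became detectable in that interval would not be looked for by a scheduled DNA test until 24 weeks after the third course began. What is at stake is patient safety, not any estimate or test.

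**Working it through.** **Inputs**
- Scheduled DNA tests in the Main Study Period: Weeks 24 and 48; stated interval 24 weeks (Table 4 with footnote 3; Table 5).
- Extension: Extension Week 0 only if on the Week 48 day, then Extension Week 24 (Table 6 starred note and footnote 4).
- Third-course start: Weeks 48 to 52 planned, Week 72 at the latest (Section 3.1). The consent route gives the same ceiling: 48 + 24 = 72.
- Window for the other retreatment laboratory results: 8 weeks (Section 3.1).

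**The plan's own figure.** Main Study Period: 48 − 24 = 24 weeks. Third course on the Week 48 day: (48 + 24) − 48 = 24 weeks. Both reproduce the stated interval.

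**Later starts.** For a third course at week s, with s above 48, the last scheduled sample is at Week 48 and the next at week s + 24:
- age of the last scheduled sample at dosing = s − 48
- interval between scheduled tests = (s + 24) − 48 = s − 24

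| Start (week) | Sample age at dosing (weeks) | Interval between scheduled tests (weeks) |
|---|---|---|
| 52 | 4 | 28 |
| 56 | 8 | 32 |
| 60 | 12 | 36 |
| 64 | 16 | 40 |
| 72 | 24 | 48 |

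At Week 72 the interval is 48 / 24 = 2 times the stated one.

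**Visit windows.** Week 48 has a window of ±5 days, and Week 24 adds ±3 days when a second course is given, because later visits are counted from that infusion. The Week 48 sample can thus fall between Day 336 − 8 = 328 and Day 336 + 8 = 344. At Day 504 (Week 72) its age is 176 to 160 days, or 25.1 to 22.9 weeks. The start at which it passes 8 weeks moves to between (328 + 56)/7 = 54.9 and (344 + 56)/7 = 57.1 weeks. The picture does not change.

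**Who can start late.** The calendar limit means that a start at week s needs enrolment at least s − 52 weeks before the last patient: more than 4 weeks for a start after Week 56, and 20 weeks for Week 72.

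**Comparison with the other repeat courses.** The second course (Week 24) and a third course on the Week 48 day each have a DNA sample scheduled that day. Those entries lack the footnote that requires assessment before infusion, and the assay is done centrally. Turnaround is not stated. Assuming no same-day result, the last result known at the second course is the Screening one. Screening runs from Day −42 to Day −1, so that result is (168 + 1)/7 = 24.1 to (168 + 42)/7 = 30 weeks old. For a same-day third course it is the Week 24 result, 48 − 24 = 24 weeks old. At a Week 72 start it is the Week 48 result, also 24 weeks old.

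**After the fix.** With a sample within 8 weeks before Extension Week 0, sample age is at most 8 weeks and the interval to Extension Week 24 at most 8 + 24 = 32 weeks, instead of 48.

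**The case against.** The strongest reply is that DNA testing here is monitoring, not a condition for dosing. The 8-week limit covers neutrophils, platelets, transaminases and IgG; the documents set no recency limit for DNA. A reader might infer that a 24-week-old sample breaks a protocol limit threefold. The text does not support that, and 8 weeks serves below only as a practical reference.

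A reader might also infer that late starters alone are dosed without a current DNA result. That is not supported either. No course requires one, and on the assumption above the last known result is as old, or older, at the second course and at a same-day third course. This part of the reply stands.

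It does not remove the difference in sampling. In those two cases blood is drawn on the dosing day, so a positive result would surface soon afterwards. A late starter has no scheduled sample until 24 weeks after dosing.

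Other safeguards are real: transaminases within 8 weeks, chemistry and physical examination before both Extension infusions and again at Extension Weeks 8, 16 and 24, the investigator's judgement on hepatic disease, DNA testing on suspected symptoms, and discussion with the sponsor before any start after Week 52. None of them schedules a DNA test.

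Read alone, the 24-week rule would make a test due at Week 72. Table 6 places it at Extension Week 24 instead, and even that reading adds no sample near dosing for starts between Weeks 56 and 72.

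**Conclusion.** The gap is in the text and is narrow. For patients enrolled on a negative DNA test, a late third course has no scheduled DNA sample at or near dosing, and the interval between scheduled tests lengthens from 24 weeks to as much as 48. Planned starts at Weeks 48 to 52 are not a concern, since the Week 48 sample is at most 4 weeks old.

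The figures rest on nominal visit weeks and on the specific Table 6 note taking precedence over the general 24-week rule. The documents give neither the number of patients enrolled on the DNA test nor the number starting late, so no patient count can be given; it is likely small. Nothing in the documents shows that any patient was harmed or dosed while DNA positive, and neither should be inferred. No efficacy or PK comparison changes. The change is still worth making because it closes a safety-monitoring gap at little cost.

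**What to change.** Amend the starred note and footnote 4 of Protocol Table 6, and their copy in SAP Appendix 1. For patients enrolled on the DNA test who start the third course more than 8 weeks after their Week 48 sample, add an HBV DNA test to the safety-criteria blood draw within 8 weeks before Extension Week 0. Have the investigator review the result before dosing. Withholding the course on a positive result would follow the entry rule in Section 6.5.8, but the protocol states no such rule for retreatment, so this is a clinical decision for the sponsor to confirm.

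The cost is one assay per affected patient and a possible wait for the central laboratory result. No extra visit should be needed: for these starts the Week 48 laboratory results are also older than 8 weeks, so a fresh draw is already required, and Table 6 footnote 1 provides that "Unscheduled visit(s) can be conducted for assessment of safety criteria until the initiation of the third course of treatment". No new SAP table is needed. If every third course has already been given, the amendment comes too late to alter conduct.
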